5.6 Study completion and discontinuation

5.6.1 Study completion and post-study treatment

A patient will complete this study when the patient has completed the End of Study (EOS) visit.

Patients, who complete the EOS visit ([Table 6-1](#)) on study drug, may be eligible for inclusion in the planned umbrella extension study (under separate protocol).

Either patients who complete their EOS visits on study drug and do not enter the umbrella extension study (planned) or patients who prematurely discontinue study drug and complete their EOS visits will enter the Safety FU period ([Table 6-2](#)) for continued follow-up.

The Safety FU will complete when all patients who entered have been followed for the stipulated period of time (for at least 36 weeks after study drug discontinuation) (see [Section 3.1.3](#)) or have withdrawn participation prematurely.

The Investigator must provide follow-up medical care for all patients who are prematurely withdrawn from the study, or must refer them for appropriate ongoing care.

5.6.2 Discontinuation of study treatment

Discontinuation of study treatment for a patient occurs when study drug is stopped earlier than the protocol planned duration, and can be initiated by either the patient or the Investigator.

The Investigator must discontinue study treatment for a given patient if, on balance, he/she believes that continuation would negatively impact the risk/benefit of trial participation.

Discontinuation of study treatment does not mean discontinuation from study. The patient should return to the site as soon as possible, after discontinuation of study drug, for EOS visit. EOS visit assessments ([Table 6-1](#)) should be completed and results recorded in the CRF. The Investigator must determine the primary reason for the patient's premature discontinuation of study treatment and record this information on the appropriate CRF.

Study treatment must be permanently discontinued under the following circumstances:

- Patient wish (withdrawal of consent [Section 5.6.3](#))
- Pregnancy (see [Section 6.5.6](#) and [Section 7.6](#))
- Use of prohibited treatment ([Table 5-1](#))
- Diagnosis of PML
- Patient with active serious infections or reactivation (e.g. tuberculosis, hepatitis B or C)
- Skin and/or mucosal reactions which raise the suspicion of severe generalized major skin reactions (Stevens-Johnson syndrome, or toxic epidermal necrolysis-Lyell's syndrome)
- Hypersensitivity to the study medication
- Any situation in which study participation might result in a safety risk to the patient
- Protocol violation that results in a significant risk to the patient's safety
- Emergence of certain adverse events, such as malignancy (except successfully treated basal cell carcinoma, *in situ* squamous cell carcinoma and *in situ* carcinoma of cervix of uterus), liver failure or, serious chronic infection (such as HIV)
- Laboratory abnormalities (e.g. liver function tests (LFT)) and abnormal test procedure as defined in [Appendix 1](#)
- Severe hypoproteinemia
- Interstitial lung disease or new onset or worsening of pulmonary symptoms, such as persistent cough and dyspnea, with or without associated fever, suspicious of interstitial lung disease
- Non-compliance with study treatment

If the patient cannot attend any further study visit(s), the site staff should maintain regular telephone contact with the patient, or with a person pre-designated by the patient, unless the patient has withdrawn informed consent (see [Section 5.6.3](#)). This telephone contact should preferably be done according to the study visit schedule.

The Investigator must also contact the IRT to register the patient's discontinuation from study treatment.

If study drug discontinuation occurs because treatment code has been broken, please refer to [Section 5.5.9](#).

Note: Patients who prematurely discontinue study drug and complete their EOS visits will enter the Safety FU period ([Table 6-2](#)) for continued follow-up (See [Section 3.1](#), [Section 5.6.1](#)). The patients should be encouraged to stay in the study and continue to follow the procedures and assessment schedule as specified in the protocol.

The Investigator should consider the benefit/risk of initiation of alternative MS therapy in terms of the patient's clinical status, local regulations, treatment guidelines and local prescribing information. In some cases, as described below, information on the patient's circulating B-cell status may be requested if in the Investigator's opinion this is needed to ensure safe switch to another MS therapy.

The duration of the washout period after last dose of study drug will depend on the type of therapy to be initiated and the patient's clinical status:

- A washout period of at least 5 months is recommended before initiation of lymphocyte depleting/suppressing/trafficking blocking agents (e.g. alemtuzumab, fingolimod, natalizumab, teriflunomide, etc.). This is in line with the expected circulating B-cell repletion course after ofatumumab discontinuation (estimated around 5 months needed for 80% repletion; see [Section 3.3](#))
- If, in the opinion of the Investigator, the safe initiation of another therapy cannot be considered without the patient's B-cell status, the Investigator must submit a request to Novartis in writing. The request of B-cell status must be justified based on clinical grounds. The Investigator must ensure data entry is complete for any such patients. The Investigator will be notified of whether or not the patient has B-cell counts at or above lower limit of normal or baseline values, whichever is lower. The detailed procedure for requesting and receiving the information on a patient's B-cell status will be provided separately.

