3.1.2 Extension part

The Extension part consists of 2 periods; **Double-blind loading dose period** and **Open-label treatment period**.

The **Double-blind loading dose period** will be applicable for patients who complete the Double-blind treatment period. All patients will receive ofatumumab 20 mg sc at Week 24; the Extension part starts with the injection of the Week 24. Patients randomized to ofatumumab in the Double-blind treatment period will receive the matching placebo sc at Week 25 and 26. Patients randomized to placebo in the Double-blind treatment period will receive ofatumumab 20 mg sc at Week 25 and 26. All patients will receive the study drug in a double-blind manner at Week 25 and 26.

The **Open-label treatment period** will begin at Week 28 and all patients will receive open-label ofatumumab 20 mg sc every 4 weeks in this period. This period will continue until the last patient is transferred to a planned umbrella extension study (under separate protocol requiring another informed consent).

Patients who prematurely discontinue study treatment will have their EOS visits as soon as possible and will be followed up for safety in the Safety FU period ([Section 3.1.3](#)) for a minimum of 36 weeks ([Table 6-2](#)). After study drug discontinuation, during Core or Extension parts, patients may initiate alternative MS therapy according to local standard of care if clinically indicated (see [Section 5.6.2](#)).

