3.1.3 Safety FU period

The **Safety FU period** ([Table 6-2](#)) will be applicable for the following patients:

- Patients who complete this study and do not enter the planned umbrella long-term extension study
- Patients who prematurely discontinue study treatment in Core or Extension part

All Safety FU visits must be scheduled relative to the date of EOS visit.

[figure not shown]
These patients will be followed for a total of at least 36 weeks after study drug discontinuation (by 36 weeks the vast majority of patients are expected to have repleted their circulating B-cells, see [Section 3.3](#)).

A longer than 36 weeks of post-treatment Safety FU period will be required for patients who have not repleted their B-cells (i.e. B-cells not back to baseline value or to lower limit of normal (LLN) whichever comes first as determined by central lab) at 36 weeks.

These patients will continue to be followed with 12-weekly assessments until their B-cell counts have repleted. To protect the study blind, the assessment of B-cell counts will be performed centrally and the Investigators and Sponsor study team will only be informed of whether or not continued follow-up is necessary.

Patients who have initiated therapy with another disease modifying/immunosuppressive therapy before the end of the 36-week follow-up will not be monitored beyond 36 weeks.

Figure 3-1 Study design

* Patients randomized to placebo in the Double-blind treatment period will receive ofatumumab 20 mg sc at Week 24, 25 and 26 as loading dose regimen. Patients randomized to ofatumumab in the Double-blind treatment period will receive ofatumumab 20 mg sc at Week 24 and the matching placebo sc at Week 25 and 26. In all patients, the extension part starts with the Week 24 injection.

** Patients who prematurely discontinue study drug or patients who do not enter the umbrella extension study will enter the Safety FU period following their EOS visits.

*** Umbrella extension study (planned) will be conducted under separate protocol.

Data cut-off 1 is defined as the date the last patient completes all the assessments for Week 24.

Data cut-off 2 is defined as the date the last patient completes all the assessments for Week 48.

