2. As needed for patients requiring prolonged B-cell plasma level monitoring ([Section 3.1](#))
3. If planned visit and End of Safety-FU occur at the same time only End of Safety-FU visit should be done. If patient is prematurely withdrawn from the Safety-FU period, the End of Safety-FU assessments should be done at time of withdrawal.
4. Female patients only: monthly urine home pregnancy testing will be conducted between clinic visits. The patient must contact the Investigator immediately in the case of a positive test for confirmatory testing at the Investigator's discretion.

* including steroids for MS relapse and newly started disease modifying therapy as applicable

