2.8.3.2 Other special lab results

Other non-routine laboratory data include pregnancy test results, CD19⁺B-cell counts, CD3⁺, CD20⁺T-cell counts, total IgG, total IgM, [REDACTED]. All data will be listed appropriately.

The B-cell counts, T-cell counts, total IgG, total IgM, [REDACTED] will be summarized using descriptive statistics by treatment group and visit-window.

In addition, number and percentage of patients with B-cells < the lower limit of normal (LLN) will be presented by treatment group and visit-window. Graphic presentation of B-cell counts distribution via box-plots will also be provided by treatment group and visit-window.

Number and percentage of patients meeting the notable low level criteria in IgG or IgM at least once will be provided by treatment group. A notably low IgG level is defined as a level that is 20% below the LLN and a notably low IgM level is defined as a level 10% below the LLN.

The following analyses will be repeated for Cut-off 2 analysis:

- Number and percentage of patients with B-cells < LLN by visit window
- Number and percentage of patients meeting the notable low level criteria in IgG and IgM
- Summary statistics

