2.8.4.4 Safety evaluation during the Safety follow-up

Safety data collected during the Safety Follow-up period includes adverse events, laboratory assessments (hematology, chemistry, urinalysis, B-cells, T-cells and Immunoglobulins) and eCSSRs. All safety assessments after study drug discontinuation will be analyzed, summarized or listed.

[figure not shown]
Safety data collected during the Safety Follow-up period will be reported separately. These analyses will include laboratory assessments including B-cell repletion, adverse events, vital signs, and eCSSRS. MS relapses and change in EDSS will also be collected. For all patients change is defined relative to the End of Study visit (EOS). Since post-treatment safety follow-up in the Safety Follow-up period may continue for up to 36 weeks (or longer if criteria for longer follow-up are met) after completion of the Treatment period study, the study report for the Core part (Screening and Double-blind treatment period) will be completed based on the completed core part i.e. based on all patients who have completed the Double-blind treatment period, and the partial data from the Safety Follow-up period available at that time. A complete analysis of the post-treatment safety follow-up will be provided in an addendum to the study report when all patients who entered the Safety Follow-up period have completed this period.

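### SAP 2.8.4.4 reports B-cell repletion after ofatumumab from all Safety FU samples and does not separate values taken after another MS drug was started (minor)

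*Protocol*

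**What the plan says.** **Switching is allowed.** Protocol 3.1.2 says that after study drug is stopped, in either part, "patients may initiate alternative MS therapy according to local standard of care if clinically indicated". Protocol 5.6.2 makes the interval depend on the type of therapy and the patient's clinical status. For one group of drugs it gives a figure, as a recommendation: "A washout period of at least 5 months is recommended before initiation of lymphocyte depleting/suppressing/trafficking blocking agents".

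**Sampling continues after a switch.** Protocol 3.1.3 states: "These patients will be followed for a total of at least 36 weeks after study drug discontinuation". Table 6-2 schedules B-cell, T-cell and total IgG/IgM samples at +W12, +W24 and +W36 from EOS, each ±14 days, then every 12 weeks if needed. The only rule tied to a new therapy is in Protocol 3.1.3, repeated in SAP 1.1: "Patients who have initiated therapy with another disease modifying/immunosuppressive therapy before the end of the 36-week follow-up will not be monitored beyond 36 weeks". It ends monitoring at Week 36, not at the switch.

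**The new drug is recorded.** The Table 6-2 footnote on concomitant medication reads "including steroids for MS relapse and newly started disease modifying therapy as applicable".

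**The analysis.** SAP 2.8.4.4 takes in every safety assessment after study drug discontinuation, to be analyzed, summarized or listed, and adds: "These analyses will include laboratory assessments including B-cell repletion, adverse events, vital signs, and eCSSRS". SAP Table 2-9 gives the Safety FU windows. Days are counted from EOS, and the only condition is that the assessment comes after the last date of study drug. For B-cells in general, SAP 2.8.3.2 plans that the "number and percentage of patients with B-cells < the lower limit of normal (LLN) will be presented by treatment group and visit-window". SAP 2.4.2.1 tabulates medications started after discontinuation but does not link them to laboratory values.

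**The concern.** A repletion summary is read as the course of B-cell recovery once ofatumumab is withdrawn. A sample taken under another lymphocyte-active drug does not measure that. Protocol Table 5-1 itself describes rituximab, ocrelizumab and obinutuzumab as B-cell depleting, so a low count after such a drug may say nothing about ofatumumab.

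The protocol partly recognizes this, since it stops following switchers for repletion after Week 36. The SAP has no matching step for values between the switch and Week 36. Elsewhere it does handle a comparable problem: SAP 2.5.2 drops MRI evaluations made within 14 days after the end of systemic steroids.

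At stake is whether a descriptive safety and pharmacodynamic table can be set against the expectations in Protocol 3.3, where modeling of an earlier study predicted 80% repletion at around 5 months and repletion of the vast majority within 9 months.

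**Working it through.** The plan gives no figure to reproduce. The check is a timeline, followed by an illustration on assumed values.

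**Inputs**
- Recommended washout: at least 5 months after last dose (Protocol 5.6.2).
- Length of a month: 28 days (Protocol 6), 30 days (SAP 2.1.1), or 365.25/12 = 30.44 days (calendar).
- Samples: +W12, +W24, +W36 from EOS, ±14 days (Protocol Table 6-2).
- Gap from last dose to EOS: not given. Assumed 0, 14 or 28 days.
- Safety cut-off: 100 days after last dose (SAP 2.1.1).

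**Step 1. Washout in days.** 5 × 28 = 140; 5 × 30 = 150; 5 × 30.44 = 152.

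**Step 2. Sampling days after EOS.**

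| Visit | Target | Visit window |
|---|---|---|
| +W12 | 12 × 7 = 84 | 70 to 98 |
| +W24 | 24 × 7 = 168 | 154 to 182 |
| +W36 | 36 × 7 = 252 | 238 to 266 |

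**Step 3. Compare.** Days since last dose = days after EOS + gap.
- Earliest in-window +W24 sample with no gap: 154 + 0 = 154, above 152. A longer gap moves it later.
- +W36 is later still.
- Latest in-window +W12 sample with the longest gap tried: 98 + 28 = 126, below 140.

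So with the washout fully observed, +W12 comes before a lymphocyte-active drug would be started, and +W24 and +W36 can come after it. This holds for every month length and gap tried. SAP Table 2-9 opens its Week 24 window at Day 127 after EOS, so an off-schedule sample in that window could still precede five months. The scheduled ones do not.

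+W12 is not always protected. The washout is only recommended, other therapies may start sooner, and a patient whose study drug was stopped because of a prohibited drug (Protocol 5.6.2, Table 5-1) can enter Safety FU already exposed.

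**Step 4. Does the 100-day cut-off remove these samples?** At their targets, +W24 and +W36 are at least 168 and 252 days after last dose, both beyond 100. If the cut-off governed, neither would be summarized. SAP 2.8 applies it only where nothing else is stated. SAP 2.8.4.4 and the Week 24 and Week 36 windows of Table 2-9 do state otherwise. The cut-off is also unrelated to a new drug.

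**Step 5. Illustration, assumed values only.** Let p be the share repleted among non-switchers, s the share who have switched, and q the share of switchers who show repletion. Pooled share = p(1 − s) + q·s. With p = 80%:

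| s | q = 0 | q = 50% |
|---|---|---|
| 10% | 72% | 77% |
| 30% | 56% | 71% |
| 50% | 40% | 65% |

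For example, 0.80 × 0.90 + 0 = 0.72, and 0.80 × 0.50 + 0.50 × 0.50 = 0.65. None of p, s or q is a forecast for this trial.

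**The case against.** **The summary is partly inferred.** SAP 2.8.4.4 allows listing as an alternative, and the percentage-below-LLN table in 2.8.3.2 does not mention Safety FU and is repeated only for Cut-off 2. This is fair: the text does not commit to that exact table for Safety FU. But 2.8.4.4 promises an analysis of B-cell repletion and Table 2-9 supplies windows, so a by-window summary is the natural reading.

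**The data for interpretation exist.** New therapy is recorded, post-discontinuation medications are tabulated and B-cell values are listed by patient. For a handful of patients a listing may be enough. This lowers the importance of the point, but nothing visible links a given value to a new drug.

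**Keeping all safety data is defensible, and a cut has its own bias.** Investigators may ask for a patient's B-cell status before starting another drug (Protocol 5.6.2), so switching may depend on repletion, and late pre-switch samples then come from selected non-switchers. This stands, and is why the restricted summary should not replace the full one.

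**Stronger readings that the documents do not support.**
- A reader might infer that a Core placebo patient who switches would look B-cell depleted in the placebo column. Final safety analyses use the Extension Safety set, in which every patient has had ofatumumab (SAP 2.1.4, 2.2). At Cut-off 1, safety data stop at the earliest of the safety cut-off, the latest visit or the Week 24 visit (SAP 2.8). Section 2.8.4.4 changes the time span but names no analysis set, so the default set stands. Grouping is by treatment actually received.
- A reader might take 10% dropout of 60 (6 patients, split 4 and 2) and conclude that one switcher moves the ofatumumab percentage by 1/4 = 25 points. The 10% is a sample-size allowance, Core dropouts are outside the Extension Safety set, and patients who withdraw consent have no further assessments (Protocol 5.6.3).
- A reader might say that Safety FU exists to show repletion. Protocol 3.2 gives safety as the reason, counts decide whether an individual needs longer follow-up (3.1.3), and no objective in Protocol 2.1 names repletion after stopping.

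**Conclusion.** The gap is real on the visible text. Two of the three fixed Safety FU samples can be taken under a new lymphocyte-active drug, and no visible rule separates those B-cell, T-cell or IgG/IgM values from recovery after ofatumumab.

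The severity is minor. The summary is descriptive, and no primary or secondary efficacy comparison is touched. The size cannot be stated because the documents give no switching rate. It is probably small in a 60-patient trial if most completers move to the umbrella study. The direction is not fixed for every drug class either, since the documents do not give each class's effect on blood counts.

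The conclusion assumes that 2.8.4.4 overrides the 100-day default and that Table 2-9 will be used for repletion. Parts of the SAP around 2.8.4.4 and in 2.13 to 2.14 are redacted or not shown, and a rule there would settle the matter.

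**What to change.** In SAP 2.8.4.4:

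- Add a summary of Safety FU B-cell, T-cell and IgG/IgM values restricted to samples taken before the first dose of any new disease-modifying or immunosuppressive therapy. Take the start date from the concomitant-medication record, with incomplete dates handled as in SAP 5.1.3.
- Show the number of patients contributing in each window.
- Present it beside the all-values summary, not instead of it.
- Flag post-switch values in the by-patient listing.
- State which medication classes count as a new therapy for this purpose, including whether short steroid courses for relapse do.

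Separate adverse-event columns before and after the switch are not needed for this defect.

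The cost is a few sentences of SAP text and one date filter on data already collected. The downside is fewer samples in the late windows, from a possibly selected group of non-switchers. No visit, treatment or clinical rule changes.

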5.6.3 Withdrawal of informed consent

Patients may voluntarily withdraw consent to participate in the study for any reason at any time. Withdrawal of consent from the study is defined as when a patient:

- Does not want to participate in the study anymore
and
 - Does not want any further visits or assessments
and
 - Does not want any further study related contacts
and
 - Does not allow analysis of already obtained biologic material

In this situation, the Investigator must make every effort (e.g. telephone, e-mail, letter) to determine the primary reason for the patient's decision to withdraw his/her consent and record this information.

Study treatment must be discontinued and no further assessments conducted, and the data that would have been collected at subsequent visits will be considered missing.

Further attempts to contact the patient are not allowed unless safety findings require communicating or follow-up.

All efforts should be made to complete the assessments prior to study withdrawal. A final evaluation (EOS) at the time of the patient's study withdrawal should be made as detailed in the schedule of assessments ([Table 6-1](#)).

5.6.4 Loss to follow-up

For patients whose status is unclear because they fail to appear for study visits without stating an intention to discontinue or withdraw, the Investigator should show "due diligence" by documenting in the source documents steps taken to contact the subject, e.g. dates of telephone calls, registered letters, etc. A patient cannot be considered as lost to follow-up until the time point of his/her planned EOS visit has passed.

